Primary Hypothesis:

Our hypothesis is that internal, controlled transverse fracture compression with modern intramedullary rod treatment of transverse tibial shaft fractures will be associated with an increased rate and time to union compared to the traditional methods of dynamic locking and backslapping.

Methods:

Inclusion Criteria

1. Skeletal Maturity
2. Closed or open diaphyseal (shaft) tibia fracture that is axially stable and will tolerate compression without shortening.
3. Treatment with Intramedullary Rod.
4. Fracture compression using one of three methods:
 - a. Dynamic locking.
 - b. Backslapping with dynamic locking.
 - c. Internal rod compression with static locking.
5. Complete inpatient and outpatient medical records and operative notes.
6. Complete radiographic and clinical follow-up for minimum one year.

Exclusion Criteria

1. Skeletally immature.
2. Metabolic Bone Disease
3. Immunosuppression
4. Pathological Fracture (Tumor, Pre-existing Infection)
5. Pre-existing Infection
6. Soft-tissue coverage not obtained within two weeks from time of injury.
7. Use of Negative Pressure Dressing to definitively manage wound.
8. Use of external or implantable bone growth stimulator.

9. Unable to Full Weight Bear immediately post-operative.

Data Points:

1. Age
2. Sex
3. Medical Comorbidity
4. Smoking Status (Yes or No)
5. Closed or Open fracture:
 - a. Wound Size (surface area)
 - b. Wound type (Gustilo Anderson and OTA)
6. Number of Surgical Debridements
7. Time to definitive closure.
8. Soft Tissue Reconstructive Procedure
9. Compartment Syndrome (Yes or No)
10. Fasciotomy (Yes or No)
11. Treatment Method:
 - a. Dynamic locking.
 - b. Backslapping with dynamic locking.
 - c. Internal rod compression with static locking.
12. Union (Yes or No)
13. Time to union (months).
14. Implant complications (Rod or Screw Breaking)
15. Loss of reduction and healing alignment on orthogonal radiographs.
16. Need for subsequent secondary treatment:
 - a. Superficial Infection (Antibiotic Treatment)
 - b. Deep Infection (Surgical Treatment)
 - c. Delayed Union (Exchange rodding, Bone grafting)
 - d. Nonunion (Exchange rodding, Bone grafting)

Methodology:

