This study will be a prospective analysis of patients with transverse tibial shaft fractures (OTA 42-A3 classification) treated with an intramedullary rod. Patients will be enrolled at a single facility (Harborview Medical Center-HMC). Patients who meet inclusion criteria will be assigned to one of the three treatment groups based on the night of presentation. Currently there are three teams that manage the trauma call at HMC (Red, Green, Blue) and alternate on a strict 1 in 3 rotation schedule. Patients that present on a night when the Red Team is on call will be treated as Group A (dynamic locking). Patients that present on a night when the Green Team is on call will be treated as Group B (backslapping with dynamic locking). Patients that present on a night when the Blue Team is on call will be treated as Group C (internal rod compression). All three methods of treatment are considered acceptable current standards of practice in the orthopedic trauma community on a local and national level. All patients will be treated similarly with respect to:

1. Open wound management
2. Immediate post-operative full weight bearing.
3. Follow-up at 6 weeks, 12 weeks, 24 weeks and 52 weeks.
 - a. Radiographic
 - b. Clinical

Union will be determined according to the modified Hammer criteria,⁶ with union considered to have occurred with bridging cortical bone on 3 or 4 cortices using orthogonal radiographic views.

Risks

There is no risk to the patient as all three treatment methods are current standard of practice both nationally and locally. All patient identifiers will be kept private. All data will be stored on a password protected database available only to the study team.

Benefits

The study performed will provide information regarding the optimal treatment strategy for transverse tibia fractures, and what the expected time to union is when using internal

compression. This information is of benefit to patients, particularly when being counseled by surgeons regarding how long they can expect before obtaining radiographic union, and what the potential reoperation rate would be.

Procedures to Ensure Confidentiality

No patient identifiers will be used during the formal study. Identifiers such as name and medical record numbers will be used to identify patients with a transverse tibia fracture, and will be stored on a password protected departmental network in a master file. Data files will be listed with subject number.

Statistical Analysis Plan

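### Exclusions 6 to 8, and item 9 where not evident at presentation, turn on events after assignment; unequal removal by arm could bias the union comparison

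*Combined protocol and SAP*

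**What the plan says.** The Methodology section states: "Patients who meet inclusion criteria will be assigned to one of the three treatment groups based on the night of presentation". The three teams "alternate on a strict 1 in 3 rotation schedule", with Red treating Group A, Green Group B and Blue Group C. Team, arm and time of assignment are therefore fixed together at presentation.

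Methods, Exclusion Criteria, lists:

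- item 6: "Soft-tissue coverage not obtained within two weeks from time of injury"
- item 7: "Use of Negative Pressure Dressing to definitively manage wound"
- item 8: "Use of external or implantable bone growth stimulator"
- item 9: "Unable to Full Weight Bear immediately post-operative"

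Methodology also says that open wound care and early full loading will be alike in all groups. Stimulator use is not on that list. Follow-up is at 6, 12, 24 and 52 weeks. Union is radiographic: bridging of three or four cortices on orthogonal views.

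The Statistical Analysis Plan names tests and a significance level of 0.05 but no analysis population. No section says when the exclusions are applied, by whom, or whether excluded patients are followed or reported.

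**The concern.** A patient can be assigned, operated on, and then leave the study because of something that happened afterwards. Rotation of on-call teams gives whatever comparability the groups have at presentation, and removing patients on later events can undo it. Because each team is one arm, any difference between teams in the timing of wound cover, choice of dressing or use of stimulators is also a difference between arms in who is removed.

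Two things are at stake. If removal differs by arm and the removed patients heal differently from the rest, the union comparison is biased. If removal is equal but those removed heal worse, union is overstated in every arm. The second matters because the Benefits section intends the results for counselling patients on healing time and reoperation.

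**Working it through.** **Timing.** Assignment is on the night of presentation. Against that:

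| Criterion | When it can be settled |
|---|---|
| Exclusion 6 | Up to two weeks after injury |
| Exclusion 7 | When the definitive wound treatment is chosen |
| Exclusion 8 | Any time; no window is given, so possibly throughout the 52 weeks |
| Exclusion 9 | After surgery as worded; sometimes evident at presentation from other injuries |
| Inclusions 3 and 4 (rod used, compression method used) | At surgery |
| Inclusion 6 (complete follow-up of at least one year) | One year or later |

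The last two rows share the problem. The protocol makes assignment conditional on inclusion criteria that cannot all be met when assignment occurs.

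**Size.** The documents give no sample size, union rate or exclusion rate, so there is no figure to reproduce. The following is an illustration, and every input is an assumption:

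- no true difference between arms
- s = share of patients with an event in items 6-9: 5%, 10%, 20%
- pL = union in those patients: 0.50 or 0.70
- pH = union in all others: 0.92
- f = fraction of affected patients actually excluded in an arm

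Observed union = [s(1 − f)pL + (1 − s)pH] / (1 − s·f).

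Largest 25% v 75% case (s = 0.20, pL = 0.50):

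- f = 0.25: (0.20 × 0.75 × 0.50 + 0.80 × 0.92) / 0.95 = 0.811 / 0.95 = 0.854
- f = 0.75: (0.20 × 0.25 × 0.50 + 0.80 × 0.92) / 0.85 = 0.761 / 0.85 = 0.895
- false difference: 4.2 points (from unrounded rates)

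| s | pL | Union, all kept | Both arms exclude 50% | Difference, 25% v 75% | Difference, 0% v 100% |
|---|---|---|---|---|---|
| 5% | 0.70 | 0.909 | 0.914 | 0.5 points | 1.1 points |
| 5% | 0.50 | 0.899 | 0.909 | 1.0 | 2.1 |
| 10% | 0.70 | 0.898 | 0.908 | 1.1 | 2.2 |
| 10% | 0.50 | 0.878 | 0.898 | 2.1 | 4.2 |
| 20% | 0.70 | 0.876 | 0.896 | 2.2 | 4.4 |
| 20% | 0.50 | 0.836 | 0.873 | 4.2 | 8.4 |

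Equal exclusion gives a difference of 0 in every row, but raises observed union in both arms (0.836 to 0.873 in the last row).

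**Effect on the test.** This uses a normal approximation to a two-sided 0.05 comparison of two arms, not Fisher's exact test, with n analysed patients per arm. The nominal chance of a significant result in the given direction is 2.5%.

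- Worst case (0.836 v 0.920): about 25%, 44% and 73% at n = 50, 100 and 200.
- 25% v 75% exclusion: from 3.1% to 9.1% at n = 50, and from 3.9% to 24% at n = 200, across the rows above.

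**The case against.** Several points on the other side are fair.

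- **Who decides.** A reader might infer that each arm's own team applies these exclusions and can shed its worst healers. The documents do not say this: they tie team to treatment group and are silent on who applies the criteria or performs soft-tissue cover. The narrower point does not need it, since bias requires only that the events occur at different rates by team.
- **Similar management.** The Methodology statement bears on items 6, 7 and 9, and one exclusion list serves all arms. If the promise is kept, removal may be close to equal. But no criteria secure it, and stimulator use lies outside it.
- **Stimulators as a sign of failure.** It is tempting to read item 8 as removing slow healers. The documents give neither timing nor indication, so use at surgery fits equally well. Data point 16 keeps and records patients who have exchange rodding or bone grafting for delayed union or nonunion, so the plan does not generally discard poor outcomes. What stands is conditional: if a stimulator is given in response to slow healing, that patient leaves while one given exchange rodding stays.
- **Prognosis.** Items 6 and 7 mainly concern open wounds. Item 9 may reflect other injuries and is not shown to mark poor union.
- **Adjustment.** Wound size and type, smoking and comorbidity are collected, so adjustment could reduce the bias in part. The plan specifies none.
- **Purpose.** Restricting to settled soft tissue and uniform loading is a recognisable way to isolate the compression method. That supports showing the restricted set, but not making it the only analysis.

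**Conclusion.** The point holds on timing. Exclusions 6 to 8, and item 9 unless evident at presentation, remove patients after assignment, and nothing in the plan retains or reports them. Bias in the comparison is possible but not demonstrated: it needs unequal removal by arm and a different union rate in those removed. The direction cannot be known in advance.

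Its size cannot be computed from the documents. On the assumptions shown it is about 0.5-4.2 points for 25% v 75% exclusion and 0 for equal exclusion. The figure of about 8 points should not be read as the expected bias: it needs one arm to exclude every affected patient and another none, with 20% affected and union of only 50% among them. Overstatement of union in every arm needs only that those removed heal worse.

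**What to change.** - Judge eligibility only on facts known at presentation. Remove items 6 to 8 as exclusions and reword item 9 to cover only what is evident then, reconciled with the Methodology statement on weight bearing.
- Apply the same principle to inclusions 3, 4 and 6. Treatment received and completeness of follow-up should not decide who is analysed, and the SAP should state how missing union is handled.
- Define the primary analysis set as every eligible assigned patient, in the assigned group, with union by the stated radiographic definition. Stimulator use should not be counted as failure to unite: that departs from the definition and could turn a team's practice into an outcome difference.
- Record the events in items 6-9 by arm, with dates and reasons. Debridements, time to wound closure and soft-tissue reconstruction are already data points.
- Report the presently restricted set as a sensitivity analysis.

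The cost is protocol and SAP wording, follow-up of some additional patients already under care, and a somewhat more heterogeneous sample. The change does not remove the confounding of team with arm, which remains a separate limitation.

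### Union Yes/No has no endpoint visit and no rule for reoperated patients, so a fracture that bridges after exchange rodding or bone grafting meets the definition as written

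*Combined protocol and SAP*

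**What the plan says.** The Primary Hypothesis compares internal compression with dynamic locking and backslapping on both the rate of union and the time to it. The relevant parts of the plan are these:

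- **Data Points, items 12 and 13:** the two outcomes are "Union (Yes or No" and "Time to union (months". Neither item names a visit or mentions reoperation.
- **Methodology, union definition:** "union considered to have occurred with bridging cortical bone on 3 or 4 cortices using orthogonal radiographic views". This is the only scoring rule.
- **Methodology, follow-up:** visits at 6, 12, 24 and 52 weeks. None is named as the endpoint for item 12.
- **Inclusion Criteria, item 6:** "Complete radiographic and clinical follow-up for minimum one year". This is a minimum, with no upper limit.
- **Data Points, item 16:** "Need for subsequent secondary treatment", which includes "Delayed Union (Exchange rodding, Bone grafting" (16c) and "Nonunion (Exchange rodding, Bone grafting" (16d). The item is not linked to items 12 or 13 and does not mention dates.
- **Statistical Analysis Plan:** Fisher's exact test for categorical variables and Mann-Whitney U for continuous ones, with no rule for reoperated patients or for patients who never unite.

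**The concern.** The trial asks which compression method gives union. A patient who needed exchange rodding or bone grafting did not get union from the assigned method alone. The union definition looks only at the film, so once that patient's fracture bridges, the definition is met. If such patients are scored Yes, two things follow. The index method is credited with the effect of the second operation, and every arm moves toward 100%, which narrows the contrast under test.

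Time to union has the same gap. A rescued patient's months to bridging would count as the assigned method's healing time, and a patient who never unites has no defined value for the Mann-Whitney test.

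The scoring of these patients is also left open, so it could be settled after the results are known. They are the patients whose index treatment failed, and so the ones who decide the comparison.

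The plan does guard against one related problem: Exclusion Criteria item 8 removes users of a bone growth stimulator. There is no equivalent rule for surgical procedures done to obtain union.

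**Working it through.** The plan gives no sample size, power, union rate or effect size, so it has no figure to reproduce. All rates, rescue fractions and arm sizes below are assumptions.

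**Step 1: apply the definition to a rescued patient.** Suppose a fracture has not bridged, is bone-grafted (item 16c or 16d), and later shows 3 bridged cortices. The Methodology rule is met. Items 12 and 13, the follow-up list and the Statistical Analysis Plan contain nothing that changes the result.

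**Step 2: effect on the difference.** Let p be the proportion united without reoperation. Let h be the fraction of the remaining patients who are reoperated, heal, are seen to have bridged during follow-up, and are scored Yes.

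Recorded rate = p + (1 − p)h

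With the same h in both arms, the recorded difference is

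[p₂ + (1 − p₂)h] − [p₁ + (1 − p₁)h] = (p₂ − p₁)(1 − h)

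The shrinkage factor 1 − h does not depend on the base rates.

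**Step 3: numbers for 85% vs 95%.**

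- h = 0: difference 10 points.
- h = 0.5: 0.85 + 0.15 × 0.5 = 0.925 and 0.95 + 0.05 × 0.5 = 0.975, difference 5 points.
- h = 0.8: 0.85 + 0.15 × 0.8 = 0.97 and 0.95 + 0.05 × 0.8 = 0.99, difference 2 points.

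**Step 4: power for one pair of arms.** Exact power of the two-sided Fisher test at 0.05, by enumeration:

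| h | Recorded rates | 50 per arm | 100 per arm |
|---|---|---|---|
| 0 | 85% vs 95% | 24.4% | 58.6% |
| 0.5 | 92.5% vs 97.5% | 6.0% | 24.8% |
| 0.8 | 97% vs 99% | 0.2% | 3.4% |

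**Step 5: sensitivity to the assumed rates.** Number per arm for 80% power, normal approximation, two-sided 0.05:

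| Union without reoperation | h = 0 | h = 0.5 | h = 0.8 |
|---|---|---|---|
| 75% vs 90% | 100 | 222 | 588 |
| 80% vs 92% | 131 | 283 | 741 |
| 85% vs 95% | 141 | 298 | 769 |

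In each row the requirement roughly doubles at h = 0.5 and rises between five- and sixfold at h = 0.8.

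**Step 6: unequal rescue.** If h differs between arms, the difference need not shrink by a common factor. With h = 0.8 in the 85% arm and 0.4 in the 95% arm, the recorded rates are 0.85 + 0.15 × 0.8 = 0.97 and 0.95 + 0.05 × 0.4 = 0.97. A true 10-point difference then disappears.

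The effect of unions first seen after 52 weeks was not quantified. The documents give no basis for it.

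**The case against.** A reader might infer that the plan scores union at any time and after any reoperation, and so counts a rescued failure as a success. The documents do not support that: no sentence says so, and the plan is silent on both points. A patient entered under 16d has been labelled a nonunion, so No on item 12 is also a possible reading. This helps less under 16c, where the label is delayed union and the same procedures are listed.

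A reader might also infer that patients followed longer get extra chances to be scored Yes. The last scheduled visit is at 52 weeks, and the one-year minimum is a condition on completeness of follow-up. Any extra follow-up would distort the comparison only if it differed between arms, which nothing shows. What stands is that 52 weeks is a natural endpoint that the plan does not name.

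It can be said, too, that failure of the index method is still visible elsewhere. Item 13 shows a late union as late, item 16 can be compared with the same Fisher test, and the Benefits section mentions the reoperation rate. That is fair, and it means that the contrast is not wholly lost. It does not settle how item 12, the outcome in the title, is to be scored.

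Finally, the powers rest wholly on assumed inputs and on one pair of arms, whereas the plan has three arms and names no pairwise comparison. They illustrate the effect and are not estimates for this trial.

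**Conclusion.** The concern holds as a gap in the outcome definition. No endpoint visit is named and reoperated patients have no scoring rule. Read literally, bridging after exchange rodding or bone grafting meets the definition of union.

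The one result that does not depend on assumed base rates is the shrinkage by 1 − h, and it requires equal rescue fractions and rescued patients scored Yes. If they are scored No, h is zero and the dilution does not arise. The plan does not say which applies, and the rule should be fixed before the arms are compared.

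**What to change.** 1. Define the primary outcome as union on the Methodology criteria by the 52-week visit, without a prior procedure to promote union.
2. Score patients reoperated for delayed union or nonunion as not united on the assigned method.
3. In the time-to-union comparison, give patients reoperated before union, or not united by 52 weeks, the worst tied rank in the Mann-Whitney test. Alternatively, use a time-to-event method that treats reoperation as failure. Some such rule is needed because Mann-Whitney is the plan's only test for this outcome and these patients have no union time.
4. Record the date of each item 16 procedure, so that its order relative to bridging is known.
5. Report union after reoperation, and union after 52 weeks, separately as descriptive outcomes.

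These changes affect scoring and analysis only, not patient care. Films and secondary procedures are already collected. The costs are somewhat lower reported union rates and the work of taking procedure dates from the records; Inclusion Criteria item 5 already requires complete records and operative notes. A mean time to union could then describe only patients united on the assigned method, so the number left out should be shown beside it.

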Union Rate of Transverse Tibia Fracture

NCT03042533

Date: 09.05.23

Union Rates of Transverse Tibia Fractures Managed with Internal Fracture Compression Through an Intramedullary Rod Compared to Standard “Backslapping”

[name]

Introduction

When compared to other fracture patterns, transverse fractures of the tibial shaft have historically been associated with an increased incidence of delayed union and nonunion when stabilized with intramedullary rods, perhaps due to the decreased cortical surface area available for healing.¹⁻⁴ As a result, some authors have recommended that simple transverse fractures of the tibial shaft be managed with plate fixation and compression of the fracture using an articulated dynamic tensioner.⁵ Open plating of the tibia requires a large incision which may be at an increased risk for soft tissue complications, particularly when operating through a high-energy injured soft tissue envelope. Furthermore, intramedullary rodding of the tibia is currently regarded as the gold standard for surgical management of tibia fractures, including transverse fractures, and as such compression plating is not considered a reasonable option unless other mitigating circumstances exist.¹

In recent years, technological advances in the design of intramedullary rods allow intraoperative, controlled compression of fractures with internal devices built in to the rod. This type of controlled compression may be beneficial when compared to traditional “backslapping” techniques, in which the amount of compression cannot be controlled or “dialed” in. After internal compression, static or dynamic locking of the rod can be accomplished as is routine when rodding typical long bone fractures. This advance poses a potential advantage when managing transverse fractures, the one fracture type most amenable to intraoperative compression to facilitate rapid bony healing.

The literature regarding intramedullary rodding of transverse tibia fractures is limited, and no literature exists comparing controlled internal compression with traditional methods of dynamic rodding or backslapping. The purpose of this analysis is to prospectively assess a consecutive cohort of patients with transverse tibial shaft fractures treated with intramedullary rodding and compressed with one of three methods: dynamic locking alone, backslapping followed by dynamic locking locking, or controlled internal

fracture compression with modern nails followed by static locking.

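### Item 14 limits implant complications to a broken rod or screw, so non-breakage problems in any group, including malfunction of the compression device only Group C relies on, are not recorded as implant complications

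*Combined protocol and SAP*

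**What the plan says.** **Data Points, item 14** reads "Implant complications (Rod or Screw Breaking". The bracket names breakage only, and the wording is the same for all three groups.

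**The component at issue.** The Introduction describes newer nails that allow "controlled compression of fractures with internal devices built in to the rod". Under Methodology, "Patients that present on a night when the Blue Team is on call will be treated as Group C (internal rod compression". The inclusion criteria and item 11 give that method as "Internal rod compression with static locking". Group A has dynamic locking alone, and Group B has backslapping with dynamic locking.

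**Neighbouring outcome items:**
- item 12: "Union (Yes or No"
- item 13: "Time to union (months"
- item 15: "Loss of reduction and healing alignment on orthogonal radiographs"
- item 16: "Need for subsequent secondary treatment", where the listed reasons are superficial infection, deep infection, delayed union and nonunion.

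**Analysis.** The Primary Hypothesis concerns union. The Statistical Analysis Plan names no implant-complication endpoint. It assigns Fisher's exact test to categorical variables in general.

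**Sources.** Inclusion criteria 5 and 6 require complete operative notes and at least one year of radiographic and clinical follow-up. Methodology sets visits at 6, 12, 24 and 52 weeks.

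**The concern.** A definition of implant complication that stops at breakage leaves out implants that fail while still in one piece. Two things are at stake.

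The first is the complication count. If item 14 is tabulated by group, as a yes/no variable would be under the general rule in the Statistical Analysis Plan, the table will describe breakage only, under a label that promises more. The Benefits section also says the study will inform patients about the potential reoperation rate. A reoperation done solely for an unbroken but failed implant fits neither item 14 nor any reason listed under item 16.

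The second is interpretation of the main result. The Introduction rests its case on compression that the surgeon can control, in contrast with backslapping. No data point records whether the device in Group C actually achieved compression. If Group C shows no advantage in union, the plan cannot tell whether compression does not help or was not delivered.

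**Working it through.** The plan states no implant-failure rate, sample size or power, so there is no figure to reproduce. The check sets possible events against the data points. The non-breakage events below are assumed examples; the documents do not list failure modes.

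| Event | Item 14 | Other items that could show it |
|---|---|---|
| Rod or screw breaks (any group) | Yes | 12, 13, 15, 16 if there are consequences |
| Internal compression device breaks (Group C) | Arguably yes, as part of the rod | As above |
| Device does not compress at surgery, nothing breaks (Group C) | No | 12, 13 if union is slow or absent; 15 if reduction or alignment suffers; 16 if infection, delayed union or nonunion is treated |
| Compression achieved, then lost without breakage (Group C) | No | As above |
| Locking screw loosens or backs out (any group) | No | As above |
| Reoperation for hardware alone, nothing broken (any group) | No | No listed reason in 16 |

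Item 11 records the treatment method, not whether it worked. Items 12, 13, 15 and 16 record consequences, not the implant event behind them.

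**Effect on a group comparison.** For group g, let
- b(g) = proportion of patients with any breakage, which item 14 records;
- s(g) = proportion with loosening or back-out but no breakage;
- d(C) = proportion of Group C with device malfunction but no breakage, loosening or back-out. In Groups A and B this term is zero, because the device is not used.

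The recorded rate is b(g). The full rate is b(g) + s(g) in A and B, and b(C) + s(C) + d(C) in C. For C against A:

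recorded difference − full difference
= [b(C) − b(A)] − [b(C) + s(C) + d(C) − b(A) − s(A)]
= s(A) − s(C) − d(C).

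The same holds for C against B, with s(B) in place of s(A).

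1. Every omitted term is zero or positive, so the recorded rate in each group can be too low but not too high.
2. Between groups, the recorded difference favours C only if d(C) > s(A) − s(C). If s(A) exceeds s(C) by more than d(C), it favours A.
3. The documents give none of these terms. The locking mode also differs (dynamic in A and B, static in C), so s(A) = s(C) cannot be taken for granted.

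**Effect on interpreting union.** Inclusion criterion 4 describes patients by the compression method used. The plan does not say how it treats a Blue Team patient in whom the device did not compress. Such a patient might stay in Group C unmarked, be recoded under item 11, or be judged ineligible. The first dilutes the contrast invisibly; the other two remove the failure from Group C.

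**The case against.** The strongest reply is that little is lost, and several parts of it stand.

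- **A broken device may already count.** The device is built in to the rod, so its breakage can reasonably be read as rod breakage. The gap is limited to events without breakage.
- **Consequences are captured.** Lost or absent compression would be expected to matter here through slower or absent union. Items 12 and 13 record that for every patient and are the outcomes of the Primary Hypothesis, so a failing device would count against Group C in the main comparison. That is right for the union result, but these items do not identify the cause.
- **The failure modes are not documented.** Compression is described as intraoperative and is followed by static locking. Nothing says that the device later loosens or loses compression. This limits any statement of size, but it does not bring such events within item 14.
- **Little formally depends on item 14.** It is one of 16 data points, and no stated hypothesis rests on it. This makes the point modest.
- **A broader count could create a new imbalance.** Backslapping is also a compression technique. Counting failure to compress at surgery as a complication of the internal device, but not of a backslap, would load a procedural failure onto Group C alone. This stands, and the fix keeps such events out of the compared total.

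A reader might infer that device failure goes wholly unrecorded, and that Group C will therefore look safer than it is. The documents do not support either step. Breakage and clinical consequences can be recorded, and omitted loosening or back-out in Groups A and B can offset or outweigh the omitted device events in C. Putting a percentage on the shift would require failure rates and group sizes that the documents do not give.

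**Conclusion.** The point holds as an outcome-definition gap, not as demonstrated bias. As worded, item 14 leaves out non-breakage implant problems in all three groups, and malfunction without breakage of the component that distinguishes Group C. Recorded rates can only be too low. By how much, and which group the comparison then favours, cannot be determined from the documents. Separately, a null union result in Group C could not be distinguished from failure to deliver compression.

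This rests on two readings. The first is that the bracket in item 14 is a definition. If it was meant only as examples, the item is undefined and needs the same clarification. The second is that loosening, back-out and device malfunction without breakage can occur; the documents neither say so nor rule it out. The change is worth making because it is cheap and does not depend on which way any bias runs.

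**What to change.** 1. Redefine item 14, identically for all three groups, as breakage, loosening or back-out of a rod (including its internal compression device) or of a screw. Record the type and date of each event from the operative notes and films already required.
2. Compare the groups on that common definition, and tabulate the types by group.
3. Record failure to achieve compression at surgery as a separate descriptive line outside the compared total. State in advance what counts as such a failure, since the plan has no measure or threshold for it.
4. State that patients with such a failure stay in their assigned group for analysis and are neither recoded under item 11 nor excluded under inclusion criterion 4.

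The cost is one more data-form line and a short written definition, with no added visits or imaging. Implant-complication counts may rise, and the descriptive line depends on how consistently the operative notes describe compression.
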